### 6.2.7. Endpoints for immunogenicity data of avelumab

All analyses described below are performed for the treatment arm containing avelumab (Arm A) unless otherwise specified.

Blood samples for avelumab immunogenicity testing will be collected at pre-dose on Day 1 of the Lead-in Phase, and Days 8, and 25 of the CRT Phase. All samples should be drawn within 2 hours before the start of avelumab or placebo infusion.

Samples positive for ADA will be analyzed for titer and may be analyzed for nAb.

Patients will be characterized into different ADA categories based on the criteria defined in Table 22.

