**Table 23. Patients Characterized Based on Neutralizing Antibody Results (nAb Status)**

Category	Definition	Patients at Risk (Denominator for Incidence)
nAb never-positive	No positive nAb results at any time point	Number of patients with at least one valid ADA result at any time point
nAb ever-positive	At least one positive nAb result at any time point	Number of patients with at least one valid ADA result at any time point
Baseline nAb positive	A positive nAb result at baseline	Number of patients with valid baseline ADA result
Treatment-induced nAb	Patient is not nAb positive at baseline and has at least one positive post-baseline nAb result; or if patient does not have a baseline sample, the patient has at least one positive post-baseline ADA result	Number of patients with at least one valid post-baseline ADA result and without positive baseline nAb result (including missing, NR)
Transient nAb response	If patients with treatment-induced nAb have (a single positive nAb result or duration between first and last positive result <16 weeks) and nAb result at the last assessment is not positive.	Number of patients with at least one ADA valid post-baseline result and without positive baseline nAb result (including missing, NR)
Persistent nAb response	If patients with treatment-induced nAb have duration between first and last positive nAb result $\geq 16$ weeks or a positive nAb result at the last assessment	Number of patients with at least one valid post-baseline ADA result and without positive baseline nAb result (including missing, NR)

ADA = antidrug antibody, nAb = neutralizing antibody, NR = no result.

The number and percentage of patients in each ADA and nAb category will be summarized.

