### 6.2.7.1. Time to and Duration of ADA and nAb response

The ADA and nAb analyses described below will include patients with treatment-induced ADA or nAb, respectively.

Time (weeks) to ADA response is defined as:

$$(\text{Date of first positive ADA result} - \text{date of first dose of avelumab} + 1)/7.$$

Time to ADA response will be summarized using simple descriptive statistics (mean, SD, median, min, max, Q1, Q3).

Duration (weeks) of ADA response is defined as:

$$(\text{Date of last positive ADA result} - \text{date of first positive ADA result} + 1)/7.$$

Duration of ADA response will be censored if:

- the last ADA assessment is positive AND patient is continuing treatment with avelumab, or

- the last ADA assessment is positive AND patient discontinued treatment with avelumab AND the last planned ADA assessment (Day 25 of the CRT Phase) is after the cut-off date.

Time to nAb response and duration of nAb response are defined similarly based on first and last positive nAb result.

Kaplan-Meier estimates (product-limit estimates) will be presented together with a summary of associated statistics including the median ADA response time with 2-sided 95% CIs. ADA response rates at different timepoints will be estimated with corresponding 2-sided 95% CIs. The CIs for the median will be calculated according to Brookmeyer and Crowley (1982) and the CIs for the survival function estimates will be derived using the log-log transformation according to Kalbfleisch and Prentice (2002) (conftype=loglog default option in SAS Proc LIFETEST) with back transformation to a CI on the untransformed scale. The estimate of the standard error will be computed using Greenwood's formula.

Duration of ADA response will be displayed graphically and analyzed using Kaplan-Meier methodology. If the number of patients with ADA response is small, the Kaplan-Meier method may not provide reliable estimates. In this case, only descriptive statistics or listings will be provided

As data permit, the analyses described above will be repeated for patients with treatment-induced nAb.

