## nAb

- nAb ever-positive versus nAb never-positive;
- nAb: treatment-induced nAb versus nAb never-positive or baseline nAb positive.

Data listings will include immunogenicity data together with relevant PK, safety and efficacy data.

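### In SAP Table 23, treatment-induced nAb for patients with no baseline sample is decided by an ADA result, so a patient can be both treatment-induced nAb and nAb never-positive

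*SAP*

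**What the plan says.** SAP 6.2.7 sets out two classification tables for immunogenicity in Arm A, Table 22 for ADA and Table 23 for nAb. Neutralizing antibody testing is a second step and is not guaranteed: "Samples positive for ADA will be analyzed for titer and may be analyzed for nAb".

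The treatment-induced row of Table 23 has two clauses. The first is "Patient is not nAb positive at baseline and has at least one positive post-baseline nAb result". The second, for patients with no baseline sample, is "or if patient does not have a baseline sample, the patient has at least one positive post-baseline ADA result". The same words stand in the treatment-induced row of Table 22.

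The two overall categories in Table 23 rest on nAb results alone. Never-positive is "No positive nAb results at any time point" and ever-positive is "At least one positive nAb result at any time point". The denominator for treatment-induced nAb keeps patients whose baseline is missing: "Number of patients with at least one valid post-baseline ADA result and without positive baseline nAb result (including missing, NR)".

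Two later sections use the category. SAP 6.2.7.1 restricts the response-time analyses to treatment-induced patients and states: "Time to nAb response and duration of nAb response are defined similarly based on first and last positive nAb result". SAP 6.2.7.3 lists, as the second of its two nAb groupings for PK and safety, "nAb: treatment-induced nAb versus nAb never-positive or baseline nAb positive".

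**The concern.** A row that defines a neutralizing-antibody category should turn on a neutralizing-antibody result. Every other definition in Table 23 does. In this one clause a positive ADA result is enough, and nothing in the SAP or protocol makes ADA-positive equivalent to nAb-positive. Protocol 9.3.2.11 asks for the percentages positive for ADA and for neutralizing antibodies to be summarized separately.

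What is at stake is the internal consistency of a listed secondary endpoint (protocol 2.2, SAP 3.2.5). A programmer who follows the text literally will produce contradictory flags for the same patient. One who quietly corrects it will depart from the SAP.

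**Working it through.** The plan states no figure that could be reproduced here, so the check is one of logic.

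**Step 1: classify every case.** Take four baseline states (no sample; ADA-negative; ADA-positive and nAb-negative; ADA-positive and nAb-positive) and four post-baseline states (ADA-negative; ADA-positive and nAb-negative; ADA-positive and nAb not tested; ADA-positive and nAb-positive). That gives 4 × 4 = 16 combinations. Each is classified by Table 23 as written, and again with nAb in place of ADA in the second clause. The four combinations with no baseline sample are:

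| Post-baseline result | Treatment-induced nAb, as written | Treatment-induced nAb, clause corrected | Overall nAb category |
|---|---|---|---|
| ADA-negative | no | no | never-positive |
| ADA-positive, nAb-negative | **yes** | no | never-positive |
| ADA-positive, nAb not tested | **yes** | no | never-positive |
| ADA-positive, nAb-positive | yes | yes | ever-positive |

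The 12 combinations with a baseline sample are governed by the first clause and do not change. So 2 of 16 combinations change class and 14 do not.

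**Step 2: follow the two affected combinations through the SAP.**
- *Contrast in 6.2.7.3.* The patient is in the treatment-induced group and, being never-positive, also in its comparator. The two groups are not disjoint.
- *Response time in 6.2.7.1.* The patient qualifies for the analysis but has no first or last positive nAb date, so time to response and duration are undefined.
- *Transient and persistent rows of Table 23.* Both need at least one positive nAb result. The patient meets neither, so the two rows need not add up to the treatment-induced total.
- *Incidence.* The patient is in the denominator under either wording, provided there is a valid post-baseline ADA result. As written the patient is also in the numerator. The error therefore runs in one direction only, upward.

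**Step 3: size.** The documents give no rate for missing baseline samples, ADA or nAb, so the number affected cannot be computed. As an illustration only, *assume* that 1% to 3% of Arm A lack a baseline sample and that 5% to 15% of those become ADA-positive. Arm A is about 640 / 2 = 320 patients.
- No baseline sample: 320 × 0.01 = 3.2 to 320 × 0.03 = 9.6.
- Of these, ADA-positive: 3.2 × 0.05 = 0.16 to 9.6 × 0.15 = 1.44.

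That is 0 to 2 patients. Under these assumptions it is an upper bound, because no reduction is made for those who are truly nAb-positive. With a denominator near 320, one patient would move the incidence by 1 / 320 = 0.3 percentage points and two by 2 / 320 = 0.6.

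**The case against.** The best defence is that Table 23 uses ADA results on purpose elsewhere. Its denominators count patients with valid ADA results, which is sensible because nAb is tested only in ADA-positive samples. That explains who counts as assessed. It does not explain why a positive ADA result should count as a positive nAb outcome, and no other definition in the table does so.

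The second defence is that the clause will rarely apply, and this stands. A pre-dose sample is scheduled for every patient on Day 1 of the Lead-in Phase, and SAP 3.4.1 treats a planned same-day sample with no recorded time as pre-dose. Only patients with no baseline sample at all reach the clause. The nAb versions of the PK and safety analyses are also planned only as data permit.

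A reader might infer more than the text supports, in four ways:
- *That these patients are counted as nAb-positive overall.* They are not. Ever-positive depends on nAb results alone, so that category and the ever-positive versus never-positive contrast in 6.2.7.3 are unaffected.
- *That the transient and persistent counts are inflated.* They are not. A patient without a positive nAb result enters neither row.
- *That the reported rate will shift visibly.* That would need rates which the documents do not give, and the illustrative range includes zero.
- *That Table 22 has the same fault.* It does not. ADA is the right analyte there. Table 22 is the likely source of the carried-over wording.

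**Conclusion.** The point holds as a drafting error that gives a wrong classification. It is confined to the second clause of the treatment-induced nAb row in Table 23 and to what depends on that row: the second nAb contrast in 6.2.7.3, the response-time analyses in 6.2.7.1, and the reconciliation of the transient and persistent rows with their parent. No other section of either document corrects the clause.

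The classification result follows from the SAP text and needs no assumed rates. The direction is certain, since treatment-induced nAb incidence can be overstated but not understated. The size is unknown, probably very small and possibly zero. The analysis is descriptive and limited to Arm A. PFS, OS and the type I error are not involved. It is worth correcting because the cost is trivial, not because it threatens a conclusion of the trial.

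**What to change.** In the treatment-induced nAb row of SAP Table 23, replace ADA with nAb in the second clause, so that a patient without a baseline sample needs a positive post-baseline nAb result. Leave the denominator column and Table 22 as they are.

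The cost is one word in the SAP, best made before database lock. No data collection or other analysis changes. The 14 combinations already classified correctly stay as they are, treatment-induced and never-positive become mutually exclusive, and every treatment-induced patient then has a positive nAb date.

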### 6.2.7.1. Time to and Duration of ADA and nAb response

The ADA and nAb analyses described below will include patients with treatment-induced ADA or nAb, respectively.

Time (weeks) to ADA response is defined as:

$$(\text{Date of first positive ADA result} - \text{date of first dose of avelumab} + 1)/7.$$

Time to ADA response will be summarized using simple descriptive statistics (mean, SD, median, min, max, Q1, Q3).

Duration (weeks) of ADA response is defined as:

$$(\text{Date of last positive ADA result} - \text{date of first positive ADA result} + 1)/7.$$

Duration of ADA response will be censored if:

- the last ADA assessment is positive AND patient is continuing treatment with avelumab, or

- the last ADA assessment is positive AND patient discontinued treatment with avelumab AND the last planned ADA assessment (Day 25 of the CRT Phase) is after the cut-off date.

Time to nAb response and duration of nAb response are defined similarly based on first and last positive nAb result.

Kaplan-Meier estimates (product-limit estimates) will be presented together with a summary of associated statistics including the median ADA response time with 2-sided 95% CIs. ADA response rates at different timepoints will be estimated with corresponding 2-sided 95% CIs. The CIs for the median will be calculated according to Brookmeyer and Crowley (1982) and the CIs for the survival function estimates will be derived using the log-log transformation according to Kalbfleisch and Prentice (2002) (conftype=loglog default option in SAS Proc LIFETEST) with back transformation to a CI on the untransformed scale. The estimate of the standard error will be computed using Greenwood's formula.

Duration of ADA response will be displayed graphically and analyzed using Kaplan-Meier methodology. If the number of patients with ADA response is small, the Kaplan-Meier method may not provide reliable estimates. In this case, only descriptive statistics or listings will be provided

As data permit, the analyses described above will be repeated for patients with treatment-induced nAb.

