| 22. | Mandatory Tumor Tissue: An archival formalin fixed, paraffin embedded (FFPE) tumor tissue block from the most recent tumor resection or biopsy must be provided for all patients enrolled in the study and submitted to the Central Laboratory prior to randomization. If an FFPE tissue block cannot be provided, 15 unstained slides (10 minimum) will be acceptable. Tumor tissue from cytologic sampling (eg, fine needle aspiration, including FFPE cell pellet material), is not adequate and should not be submitted. Tumor tissue collected in China (via slides) will not be retained and will be examined for PD-L1 expression and CD8 lymphocyte infiltration by immunochemistry, tumor mutational burden, and immune repertoire by TCR analysis. |
| 23. | Optional De Novo Tumor Biopsy – Lead-in Phase: An optional tumor biopsy, to be collected 4 to 7 days following the single dose of avelumab in the Lead-in Phase, is requested for analysis of potential biomarkers of response. The de novo biopsy should be FFPE per routine (see Study Manual), and the resulting tissue block(s) submitted to the central laboratory.   |
| 24. | Anti-Avelumab Antibodies (Anti-Drug Antibodies, ADAs) and Neutralizing Antibodies (Nab): One blood sample (3.5 mL at each time point) for ADA will be collected at pre-dose on Day 1 of the Lead-in Phase, and Days 8, and 25 of the CRT Phase. All samples should be drawn within 2 hours before the start of avelumab or placebo infusion. All samples that are positive for ADA may also undergo characterization for Nab.  |

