20. **Anti-Avelumab ADAs and Nab:** One blood sample (3.5 mL) for anti-avelumab antibodies will be collected at on Day 1 of Cycles 1 and 2 of the Maintenance Phase. All samples should be drawn within 2 hours before the start of avelumab or placebo infusion. Thereafter a pre-dose sample will be taken every 3 cycles (eg, Cycles 5, 8, 11) while a patient remains on treatment. A single sample will be taken at both EOT and 30 days post-EOT. All samples that are positive for ADA may also undergo characterization for Nab.

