**Table 22. Patients Characterized Based on Anti-Drug Antibody Results (ADA Status)**

Category	Definition	Patients at Risk (Denominator for Incidence)
ADA never-positive	No positive ADA results at any time point; ADA-negative patients (titer < cutpoint)	Number of patients with at least one valid ADA result at any time point
ADA ever-positive	At least one positive ADA result at any time point; ADA-positive patients (titer ≥ cutpoint)	Number of patients with at least one valid ADA result at any time point
Baseline ADA positive	A positive ADA result at baseline	Number of patients with valid baseline ADA result
Treatment-boosted ADA	A positive ADA result at baseline and the titer ≥ 8×baseline titer at least once after treatment with avelumab	Number of patients with valid baseline ADA results and at least one valid post-baseline ADA result
Treatment-induced ADA	Patient is ADA-negative at baseline and has at least one positive post-baseline ADA result; or if patient does not have a baseline sample, the patient has at least one positive post-baseline ADA result	Number of patients with at least one valid post-baseline ADA result and without positive baseline ADA result (including missing, NR)
Transient ADA response	If patients with treatment-induced ADA have (a single positive ADA result or duration between first and last positive result <16 weeks) and ADA result at the last assessment is not positive.	Number of patients with at least one valid post-baseline ADA result and without positive baseline ADA result (including missing, NR)
Persistent ADA response	If patients with treatment-induced ADA have duration between first and last positive ADA result ≥16 weeks or a positive ADA result at the last assessment	Number of patients with at least one valid post-baseline ADA result and without positive baseline ADA result (including missing, NR)

ADA: anti-drug antibody, NR = not reportable.

Patients will be characterized into different nAb categories based on the criteria in Table 23. For nAb, treatment-boosted is not applicable since no titer result is available.

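### The SAP's censoring rule for ADA duration takes CRT Day 25 as the last planned sample, but the protocol samples until 30 days after end of treatment, so the rule's second criterion is inoperative

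*SAP*

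**What the plan says.** **SAP.** Section 6.2.7 says that ADA samples are "collected at pre-dose on Day 1 of the Lead-in Phase, and Days 8, and 25 of the CRT Phase" and lists no later visit. Section 6.2.7.1 defines duration of ADA response as the span from first to last positive result and censors it in two situations, both requiring a positive last result. The first is that the patient is still receiving avelumab. The second is that the patient has stopped avelumab and "the last planned ADA assessment (Day 25 of the CRT Phase) is after the cut-off date". The nAb duration is defined in the same way.

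**Protocol.** Table 2, footnote 24 gives the same three early visits as the SAP. Table 3, footnote 20 then extends ADA sampling into Maintenance: at the start of the first two cycles, and at three-cycle intervals after that for as long as treatment lasts. It closes the schedule with two further draws: "A single sample will be taken at both EOT and 30 days post-EOT".

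Protocol 7.4.1 also places ADA monitoring in both the treatment and follow-up periods, and 9.3.2.11 plans an ADA summary by phase that includes Maintenance.

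**The concern.** The SAP appears to have carried over the Lead-in and CRT sampling visits and omitted those in the second schedule table. The omission then became part of the censoring rule. The second criterion should protect against treating a response as finished when a planned sample that could show it continuing has not yet been taken. Tied to CRT Day 25, it gives no such protection. A patient who recently stopped avelumab, was positive at the last sample and has the EOT or 30-day sample outstanding at the cut-off enters the Kaplan-Meier analysis as an event. Turning censored observations into events lowers the curve and shortens the estimated duration.

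The short list also conflicts with other parts of the SAP. Tables 22 and 23 use a 16-week threshold for persistent response, and 6.2.7.2 tabulates ADA durations up to more than 25 weeks.

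**Working it through.** **1. Where Day 25 comes from.** It is the last entry in the list in SAP 6.2.7 and in protocol Table 2, footnote 24. The worked example in SAP 6.2.7.3 also reproduces from those visits (8 − 25 = −17). It does not reproduce from the full protocol schedule, where the last planned sample is 30 days post-EOT.

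**2. When Day 25 falls.** Inputs: first dose 0 to 3 days after randomization (protocol 5.1); Lead-in of 7 days (protocol Table 4); Day 25 dose allowed from Day 24 to Day 29 (protocol section 5); 1 month = 30.4375 days (SAP 5.2.8). Days from randomization = dosing lag + 7 + (CRT day − 1).
- No lag, Day 25: 0 + 7 + 24 = 31 days = 1.0 month.
- 3-day lag, Day 29: 3 + 7 + 28 = 38 days = 1.25 months.

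**3. When the cut-offs fall.** Accrual is assumed to take 22 months (SAP 5.1.1). SAP Table 7 projects the PFS interim at month 34 under HR = 1 and month 38 under HR = 0.68. Relative to the last randomization, that is 34 − 22 = 12 months and 38 − 22 = 16 months. The final PFS cut-off is at least 24 months after the last randomization (SAP section 2). Day 25 therefore precedes every planned cut-off for essentially every patient, and the second criterion is not met.

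**4. When the last planned sample really falls.** For a patient completing treatment on schedule, counting from first dose: 7 (Lead-in) + 63 (CRT Phase) + 364 (52 weeks of Maintenance) = 434 days = 14.26 months to the end of treatment. Adding 30 days gives 464 days = 15.24 months. Counting from the last dose instead, or adding the dosing lag and visit window, moves the last sample within about 14.8 to 15.5 months.

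**5. Completers affected at month 34.** The second criterion matters only for patients who have stopped avelumab, so those at issue are between 14.26 and 15.24 months from randomization. They were randomized between 34 − 15.24 = 18.76 and 34 − 14.26 = 19.74 months. The documents say accrual is non-uniform but do not give its shape, so two assumptions are shown:
- Uniform: (30/30.4375)/22 = 0.986/22 = 4.5%.
- Linear ramp, cumulative accrual (t/22)²: (19.74² − 18.76²)/22² = 7.8%.

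With 640/2 = 320 patients in Arm A, this is about 14 to 25 patients before requiring treatment-induced ADA and a positive last sample. The documents give no ADA rate for this trial.

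**6. Month 38.** 38 − 15.24 = 22.76, which is after accrual ends at month 22. Every on-schedule completer has already reached the 30-day sample.

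**7. What the SAP's short list could yield.** Duration = (last positive − first positive + 1)/7. With a negative baseline, the earliest positive is CRT Day 8.
- To Day 25: (25 − 8 + 1)/7 = 2.6 weeks.
- To Day 29: (29 − 8 + 1)/7 = 3.1 weeks.

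Without CRT delays, neither a 16-week span nor any of the bins above 5 weeks in SAP 6.2.7.2 could occur. On the protocol schedule, Maintenance Cycle 5 Day 1 is 7 + 63 + 4 × 28 = 182 days after first dose. CRT Day 8 is 14 days after first dose, so the gap is 168 days = 24 weeks.

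**The case against.** The strongest reply is that little depends on this, and much of that reply stands.

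- **Most patients with a pending sample are already protected.** A reader might count everyone randomized after month 18.76 as affected at month 34: 1 − 18.76/22 = 15% under uniform accrual, or 1 − (18.76/22)² = 27% under the ramp. That overstates the effect. On-schedule patients randomized after month 19.74 are still on treatment and are censored by the first criterion, which leaves 4.5% to 7.8%.
- **The persistent category is not empty.** A reader might infer that the short list makes it impossible. Table 22 also accepts "a positive ADA result at the last assessment", which can occur with CRT samples alone. Only the 16-week route is closed.
- **The durations themselves do not change.** Last minus first positive date is the same either way; only the event or censoring flag in the Kaplan-Meier analysis differs. The titer cross-tabulation in 6.2.7.2 ignores censoring, and the Table 22 categories do not use the rule.
- **No affected analysis is scheduled at the interim.** SAP 7.1 describes PFS and OS analyses there, with unblinded results restricted to the independent statistician and the E-DMC unless PFS crosses for efficacy or the study must be terminated. An effect at month 34 therefore requires the interim to become the reporting cut-off. This is possible: Table 7 gives a 0.7679 probability of crossing the futility boundary at month 34 under HR = 1, although that boundary is non-binding.
- **The protocol governs sampling.** The SAP is based on it, and Table 22 refers to results at any time point, so Maintenance samples are not formally excluded.

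None of this rescues the stated rule, which contradicts the protocol and has no practical effect.

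**Conclusion.** The point holds as a drafting error in a secondary, descriptive analysis. The SAP names the wrong last planned ADA sample, and its second censoring criterion is inoperative at every planned cut-off. The bias is downward and affects only the Kaplan-Meier estimates of ADA and nAb duration. It matters chiefly if reporting is triggered at a month-34 interim. About 4.5% to 7.8% of patients are then on-schedule completers in the 30-day window, plus recent early discontinuers, before the Arm A, treatment-induced and positive-last-sample restrictions. At month 38 or later almost none are affected, apart from patients with marked treatment delays.

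These figures assume the projected analysis times, 22 months of accrual in one of the two shapes shown, and treatment on schedule. The documents support no effect on PFS, OS, alpha or sample size. The 16-week threshold and longer duration bins fit the protocol schedule, which suggests an oversight rather than a decision to stop sampling early.

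**What to change.** In SAP 6.2.7.1, replace the parenthetical reference to CRT Day 25 with 30 days post-EOT. In SAP 6.2.7, give the full ADA schedule from protocol Table 2, footnote 24 and Table 3, footnote 20: Lead-in Day 1; CRT Days 8 and 25; Day 1 of Maintenance Cycles 1 and 2, then every 3 cycles; EOT; and 30 days post-EOT.

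Treat the sampling list in SAP 6.2.7.3 separately. It stops at CRT Day 25 too, and a reader might be inclined to insert the ADA schedule there. That would be wrong, because the list covers avelumab PK samples and distinguishes pre-dose from end-of-infusion draws. Align it with the protocol's PK schedule (Table 2, footnote 19 and Table 3, footnote 17).

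The cost is SAP wording only, with no new samples, visits or analyses.
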